
293 **2.6** Late evidence of fibrosis progression after LDLT or DDLT for HCV

HCV recurrence after liver transplantation is universal in patients who are viremic pre-operatively.

295 Chronic hepatitis evolves to cirrhosis at a variable rate, but more rapidly than in non-transplant

296 patients; ~20% of patients develop cirrhosis within 5 years of LT. Initial studies suggested that

- 297 outcomes for recipients of LDLT with HCV were inferior to recipients of DDLT with HCV, with
- 298 higher rates of graft loss, more frequent occurrence of severe cholestatic hepatitis, and higher rates

of cirrhosis⁵³⁻⁵⁵. However, subsequent studies, including results from the A2ALL-1 Study cohort, 299

300 showed similar graft and patient survival once centers had mastered the technical aspects of the

LDLT procedure^{45,56-59}. In the A2ALL-1 cohort of 181 LDLT and 94 DDLT HCV-infected 301 302 recipients, overall 3-year unadjusted graft survival was 68% for LDLT versus 80% for DDLT (p =

303 0.04), respectively. However, when analysis was restricted to LDLTs after the first 20 cases at each

304 center, graft survival in recipients of LDLT and DDLT were not significantly different, 79% versus

- 80%, respectively $(p=0.74)^{56}$. A significant limitation of the first A2ALL study is the fact that 305
- 306 protocol liver biopsies were missing in approximately one third of recipients, and follow-up liver
- 307 biopsies obtained more than 3 years post-transplant comprised only a small fraction of the liver
- 308 biopsies available for analysis.
- 309 Initial studies of HCV disease progression reported higher rates of severe HCV recurrence in LDLT
- 310 compared to DDLT recipients, observations which have not been confirmed in subsequent studies.
- 311 However, studies to date are limited in the duration of follow-up, with most reporting disease
- 312 progression up to only 2-3 years post-LT, and in relatively small patient populations. Thus, the
- 313 outcome of HCV recurrence after LDLT vs. DDLT requires further study for longer periods of
- 314 follow-up and in larger patient populations; patients enrolled in Retro and Cohort A2ALL-1 are
- 315 ideally suited to answer this critical question.
- Clinical factors influencing the rate of HCV disease progression and risk of graft loss have been well-described in DDLT, but not LDLT, recipients⁶⁰. The factors most consistently linked with 316
- 317

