- 1070 In this study, we will recruit approximately 500 male and female HCV-infected adult liver transplant
- 1071 recipients from the 6 continuing A2ALL-1 centers (from those patients enrolled in the A2ALL-1
- 1072 Cohort study), and from those concurrently transplanted at new A2ALL-2 centers (University of 1073 Toronto, University of Pittsburgh, Lahey Clinic).
- 1074 In addition to those listed in Sections 4.1.2.1 and 4.1.2.2, the following inclusion and exclusion 1075 criteria apply to potential subjects with recurrent HCV.
- 1076 4.5.2.1 Inclusion criteria
- Continuing centers will include LDLT and DDLT recipients enrolled in A2ALL-1 with
 evidence of HCV at transplantation.
- New centers will include transplanted patients (between January 1998 and August 31, 2010)
 who had at least one potential living donor who underwent an initial evaluation history and
 physical examination at the center and had evidence of HCV at transplantation.

- Recipients must have survived at least 90 days without retransplantation.
- **4.5.2.2 Exclusion criteria**
- Documented SVR prior to transplant (non-detectable HCV RNA at least six months after end of treatment)
- Co-infection with hepatitis B virus (HBsAg-positive) before transplant
- 1087 Co-infection with HIV
- Receipt of a graft from an HCV-infected donor
- LDLT was one of the first 20 cases at the site
- 1090 **4.5.2.3** Subjects who will be approached for ≥ 3 year post-transplant liver biopsy

Surviving subjects who meet the inclusion criteria and none of the exclusion criteria listed in
Sections 4.5.2.1 and 4.5.2.2 will be approached for a liver biopsy unless they have one of the
following conditions: re-transplantation, clinical evidence of decompensated cirrhosis, cirrhosis
documented on previous biopsy, liver biopsy performed within the past 12 months, or coagulopathy
precluding a liver biopsy. Those subjects who had a biopsy in the past 12 months or had cirrhosis on
a previous biopsy will have the biopsies re-read by the A2ALL-2 central pathologist.

10974.5.2.4Inclusion of deceased subjects, retransplanted subjects, and those who do not1098undergo the ≥3 year post-transplant liver biopsy

1099 Inclusion of these subjects will be critical to avoid a survivor bias and also to meet the required

- 1100 sample size (Table 4). In order to collect the most robust representation of outcomes in LDLT and
- 1101 DDLT recipients, clinical information as well as liver histology data obtained post-transplant will be

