- 1102 extracted. Data from recipients who are already deceased, are lost to follow-up, re-transplanted or
- 1103 have clinical evidence of graft failure will be collected retrospectively under a Waiver of Consent.
- 1104 Former Cohort subjects who have been re-transplanted and were ineligible for the main core
- 1105 protocol will be approached and consented for the HCV aim only. Those that are found to be
- 1106 deceased or lost-to-follow-up will have chart review conducted under a Waiver of Consent as
- 1107 described above. Gap-era Core subjects who had previously reached the endpoint of re-transplant 1108 will be approached for consent into the HCV sub-study so that their charts can be reviewed. If they
- are lost to follow-up, their charts will be reviewed under a Waiver of Consent as described above.

1110 **4.5.3 Data elements**

1117

- Since we have previously shown that center experience is an important determinant of outcome after LDLT for HCV, statistical analysis of outcome will adjust for center experience. New A2ALL sites
- 1113 will therefore identify those LDLT recipients done with center experience >20 cases.
- 1114 In addition to the data elements listed in Section 4.1.3, the following additional data will be 1115 collected:
- 1116 Living Donors (characteristics at donation)
 - Age, race, gender, diabetes, BMI, relationship to recipient
- **Deceased Donors (characteristics at transplant)**
- Age, race, gender, diabetes, BMI, relationship to recipient, cause of death, donation after
 cardiac death (DCD) status

1121	٠	Recip	ients
1122		0	Labs (albumin, AST, ALT, bilirubin, creatinine, INR) at the time of transplant,
1123			diabetes, BMI, cold and warm ischemia times, treated acute rejection episodes
1124			(dates/treatment), CMV disease (dates/treatment), HCV treatment (dates, drug
1125			regimen, date of SVR if applicable), immunosuppression regimen at day 0-7, at 12
1126			months post-transplant, and at time of biopsy, case number (for LDLTs).
1127		0	Biosamples – collected once, at the time of liver biopsy or after activation into the
1128			HCV component of the study (> 3years post-txp) – serum, plasma, whole blood for
1129			DNA extraction (if not previously collected as part of Aim 2). These samples will be
1130			stored at the NIDDK Biosample Repository for future studies on HCV recurrence
1131			after liver transplantation.
1132	٠	Outco	omes: Severity measures (with dates)
1133		0	Liver biopsy (Ishak score)

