1174 Patients with a biopsy documenting cirrhosis will be considered to have met the primary endpoint at some time prior to biopsy (i.e., left-censored data). Those with a biopsy documenting no cirrhosis 1175 will not vet have crossed the threshold (i.e., right-censored data). If additional biopsies are available, 1176 1177 then we may be able to isolate the interval in which cirrhosis occurred as between the last biopsy 1178 documenting no cirrhosis and the first biopsy documenting cirrhosis (interval-censored data). If 1179 biopsy is not available, liver stiffness measurement by transient elastography will be used to 1180 determine if primary endpoint of cirrhosis was met. In the absence of both biopsy and liver stiffness measurement, primary endpoint will be determined based on clinical and laboratory criteria 1181 1182 contained in the data elements listed in Section 4.5.3. This information will also be used to 1183 determine if the primary endpoint was reached in patients who died or who had been re-transplanted. Data will be reviewed by the HCV Adjudication Committee to determine if criteria for cirrhosis 1184 1185 were met and if death or graft loss was HCV-related. The cumulative distribution (or survival) function for time from transplant to cirrhosis will be estimated using either parametric models or 1186 nonparametric (Turnbull estimator) methods. To test for a difference in this distribution between 1187

- 1188 LDLT and DDLT, adjusting for covariates such as age and MELD score, parametric regression
- 1189 models (e.g., using SAS Proc Lifereg), or discrete survival analysis methods (e.g., using SAS Proc
- 1190 Genmod) will be used.
- 1191 In addition, times to patient death and graft failure will be analyzed as right-censored outcomes,
- 1192 using standard survival methods (Kaplan-Meier estimates, log rank tests, and Cox regression). Non-
- 1193 Markov multistate models⁷³ will be considered if feasible with the available data.
- 1194 Validation of transient elastography will be performed based on the subset of patient who undergo
- both transient elastography and biopsy within 90 days of each other. The correlation coefficient
- between transient elastography measure and Ishak score from biopsy will be calculated. A
- calibration model will be fit to convert transient elastography values into Ishak equivalents. A strong
- 1198 correlation (e.g., 0.7 or higher) would be expected if the two methods are to be considered

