8.4 APPENDIX D: Potential Subjects for Enrollment into the Core Protocol

occurred in the Gap Era**(must be three years post-transplant for the HCV Study)						
New Subjects (all centers)	Enroll into Core Protocol?	Enroll into HRQOL Sub- study?	HCV Study	Donor Pain Study	Existing Data Sources	Potential Data Entry Methods
Actual Donors shortly Pre-donation	YES	YES	NO	YES	NONE	New Data Entry
LDLT Recipients shortly Pre-transplant	YES	NO	NO	NO	NONE	New Data Entry
Donors whose donation occurred in the Gap Era**	YES	NO	NO	NO	NONE	Upload/New Data Entry
LDLT Recipients whose transplant occurred in the Gap Era**(must be three years post-transplant for the HCV Study)	YES	NO	YES	NO	NONE	Upload/New Data Entry
Donors that Donated Prior to the Gap Era** (new centers only)	NO	YES	NO	NO	NONE	Upload/New Data Entry
LDLT Recipients whose transplant occurred during the Cohort Era****	NO	NO	YES	NO	NONE	Upload/New Data Entry
DDLT Recipients with HCV whose transplant occurred during the Cohort Era**** AND had a living donor evaluated(must be three years post- transplant for the HCV Study).	NO	NO	YES	NO	NONE	Upload/New Data Entry

* End of Cohort Enrollment = August 31, 2009

** Gap Era = September 1, 2009 - Site Initiation for Core Protocol (will vary by site)

*** Data for former A2ALL subjects exists in BioDBx up through August 31, 2010. All subjects will be post-

transplant/donation. Additional data for the time period September 1, 2010-Site Initiation for Core Protocol will have to be manually entered or uploaded via spreadsheet.

****Cohort Era = March 1, 2003 – Sept. 1, 2010

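### Aim 5 drops each site's first 20 LDLT with no matching limit on DDLT, which can unbalance calendar time between the graft groups, and the stated adjustment for centre experience cannot correct it

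*Protocol*

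**What the plan says.** Protocol 4.5.2.2 lists among the Aim 5 exclusions: "LDLT was one of the first 20 cases at the site". No exclusion in that list sets a matching limit for DDLT.

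Eligibility by date is the same for both graft types. For new sites, 4.5.2.1 reads: "New centers will include transplanted patients (between January 1998 and August 31, 2010". For continuing sites it reads: "Continuing centers will include LDLT and DDLT recipients enrolled in A2ALL-1 with", followed by evidence of HCV at transplantation. Appendix D gives another window for new-centre recipients in the HCV study: "Cohort Era = March 1, 2003 – Sept. 1, 2010".

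On adjustment, 4.5.3 says that "statistical analysis of outcome will adjust for center experience" and asks new sites to identify LDLT done with experience of more than 20 cases. The experience variable in its recipient data list is "case number (for LDLTs"). The model in 4.5.5 is described as testing for a difference between "LDLT and DDLT, adjusting for covariates such as age and MELD score, parametric regression" models or discrete survival methods. Transplant year is not named.

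**The concern.** The learning-curve exclusion is sensible in itself. Section 2.6 shows why it was adopted: 3-year graft survival was 68% for LDLT against 80% for DDLT overall, and 79% against 80% once LDLT was limited to later cases ("However, when analysis was restricted to LDLTs after the first 20 cases at each" center).

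The difficulty is that the rule acts on one group. Within a site, every transplant before the 20th LDLT that stays in the analysis is a DDLT. Immunosuppression and post-transplant HCV treatment, both recorded under 4.5.3, can change over a window of more than 12 years. If the risk of cirrhosis changed with them, part of any LDLT v DDLT difference could reflect when patients were transplanted and not which graft they received. The protocol takes this hazard seriously elsewhere: 4.3.1 gives possible era effects as one reason to leave out donors from before 2002. Aim 5 states no such protection.

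**Working it through.** **No plan figure to reproduce.** The protocol gives no transplant dates by graft type and no date for any site's 20th LDLT. What follows is logic plus an illustration whose inputs are assumptions.

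**1. Can the stated adjustment work?** Case number has no value for a DDLT recipient, so it cannot align the two groups. The flag for more than 20 cases is always true for an LDLT kept in the analysis. A covariate that is undefined in one group and constant in the other adjusts nothing between them.

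**2. How far does the exclusion move LDLT?** Window under 4.5.2.1: January 1998 to August 2010 = 152 months = 12.67 years (T). Let t be the part of the window, in years, that precedes the 20th LDLT (assumed 1 to 4). With uniform accrual in both groups, the LDLT mean transplant date becomes later than the DDLT mean by t/2. With no true graft effect and a cirrhosis hazard multiplied by r per calendar year, the spurious LDLT:DDLT hazard ratio is about r^(t/2).

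| t (years) | Shift t/2 | r = 0.90 | r = 0.95 | r = 1.00 | r = 1.05 |
|---|---|---|---|---|---|
| 1 | 0.5 | 0.949 | 0.975 | 1.00 | 1.025 |
| 2 | 1.0 | 0.900 | 0.950 | 1.00 | 1.050 |
| 3 | 1.5 | 0.854 | 0.926 | 1.00 | 1.076 |
| 4 | 2.0 | 0.810 | 0.902 | 1.00 | 1.103 |

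**3. Is LDLT always the later group?** No. Section 2.1 reports that US adult LDLT numbers fell modestly between 2002 and 2008. As a deliberately strong version, let the LDLT accrual density be 1 - 1.5(x/T - 0.5) at time x. Before any exclusion its mean lies 1.5 × 12.67/12 = 1.58 years before that of flat DDLT accrual. LDLT mean minus DDLT mean, in years:

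| Accrual assumed | t = 0 | t = 1 | t = 2 | t = 3 | t = 4 |
|---|---|---|---|---|---|
| LDLT falling, DDLT flat | -1.58 | -0.93 | -0.27 | +0.38 | +1.03 |
| LDLT falling, DDLT rising | -3.17 | -2.51 | -1.86 | -1.20 | -0.55 |

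In both rows the exclusion moves LDLT later, but where LDLT started as the earlier group it can bring the groups closer together. The sign of the spurious effect can reverse: with r = 0.90, t = 1 gives 0.90^(-0.93) = 1.10 in the first row and 0.90^(-2.51) = 1.30 in the second.

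**4. Does the window matter?** January 1998 to March 2003 is 62 months, or 5.2 years. A new site that reached its 20th LDLT 1 to 4 years after January 1998 did so before March 2003. Under the Appendix D start, t is then 0 and the exclusion removes nobody inside the window. New sites matter: Table 5 lists 112 + 14 + 21 = 147 DDLT at Toronto, Lahey and Pittsburgh, about two thirds of the stated 221 (the site counts as they appear sum to 230).

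**5. What would restricting DDLT cost?** Assume 221 DDLT spread evenly over T; the number kept is 221(1 - t/12.67). Power is for 12% v 5% with 304 LDLT, two-sided 0.05: Φ{[0.07 - 1.96√(p̄q̄(1/n₁+1/n₂))] / √(p₁q₁/n₁+p₂q₂/n₂)}. At t = 0 this is Φ[(0.07 - 0.0497)/0.0237] = 0.80.

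| t | DDLT kept | Power |
|---|---|---|
| 0 | 221 | 0.80 |
| 1 | 204 | 0.78 |
| 2 | 186 | 0.755 |
| 3 | 169 | 0.72 |
| 4 | 151 | 0.68 |

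DDLT falls below 200 once t exceeds (1 - 200/221) × 12.67 = 1.2 years. The same formula gives 0.71 for the plan's 200 per group, not its stated 92%. That is a separate matter, so only the change down the column should be read here.

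**The case against.** The strongest reply is that an unnamed covariate is no defect. The list in 4.5.5 is open, a statistical analysis plan may exist, and transplant date is inherent in the time-to-event outcome. That is fair as far as the covariate list goes. It does not dispose of the point, because the imbalance comes from an eligibility rule in the protocol and the one remedy the protocol states cannot act on it.

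A reader might go further and infer that the DDLT group is older, so that era differences favour the stated hypothesis of slower progression after LDLT. The document does not support this:

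- No transplant dates are given, and the sign depends on accrual (step 3).
- A new-centre DDLT recipient must have had a potential living donor evaluated at that centre (4.5.1, 4.5.2.1), so none can predate its living-donor evaluations.
- The exclusion is per site. An early-year LDLT at a centre already past 20 cases stays in, so early years are not DDLT-only across the nine sites.
- The unchanged 80% for DDLT in 2.6 is consistent with DDLT not having been restricted. It concerns graft survival, not cirrhosis, and shows no era effect.
- One could assume that 10-30% of DDLT precede the 20th LDLT and carry 1.3-2.0 times the later hazard, which inflates the DDLT hazard by 1 + s(HR - 1) = 1.03 to 1.30. Those inputs are not in the protocol and admit only one direction.

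The recorded HCV treatment and immunosuppression data, and central re-reading of biopsies (4.5.1), limit some era effects. They do not replace transplant date: the first two are largely post-transplant variables, and re-reading addresses only drift in histology.

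**Conclusion.** The point holds in a limited form. The first-20 rule applies to LDLT alone, shifts that group later than it would otherwise be, and can unbalance calendar time in the primary Aim 5 comparison; adjustment for centre experience as specified cannot correct this. Direction and size are unknown. They depend on accrual by graft type, the date of each site's 20th LDLT, any era trend in cirrhosis risk, and which new-centre start date applies. The illustrative hazard ratios (0.81 to 1.30 with no graft effect) show that the issue could be negligible or material; they are not estimates of the bias in this study.

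**What to change.** 1. In 4.5.5, name transplant date (calendar year), with centre, as a prespecified covariate in the LDLT v DDLT model for time to cirrhosis. The date is already needed for the outcome, so this costs no patients.
2. Report the distribution of transplant dates by graft type, overall and by centre, so that the direction of any imbalance is visible.
3. Reconcile the new-centre start date in 4.5.2.1 (January 1998) with Appendix D (March 2003).
4. As a sensitivity analysis only, restrict DDLT at each centre to transplants on or after the date of its 21st LDLT. This checks the covariate adjustment over years in which a centre contributes only DDLT. The cost is sample size: 4.5.4 says that nearly all DDLT are needed, and step 5 shows that the group may fall below 200. Deceased and retransplanted recipients, included under 4.5.2.4 but not counted in Table 5, may offset part of the loss.

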1174 Patients with a biopsy documenting cirrhosis will be considered to have met the primary endpoint at some time prior to biopsy (i.e., left-censored data). Those with a biopsy documenting no cirrhosis 1175 will not vet have crossed the threshold (i.e., right-censored data). If additional biopsies are available, 1176 1177 then we may be able to isolate the interval in which cirrhosis occurred as between the last biopsy 1178 documenting no cirrhosis and the first biopsy documenting cirrhosis (interval-censored data). If 1179 biopsy is not available, liver stiffness measurement by transient elastography will be used to 1180 determine if primary endpoint of cirrhosis was met. In the absence of both biopsy and liver stiffness measurement, primary endpoint will be determined based on clinical and laboratory criteria 1181 1182 contained in the data elements listed in Section 4.5.3. This information will also be used to 1183 determine if the primary endpoint was reached in patients who died or who had been re-transplanted. Data will be reviewed by the HCV Adjudication Committee to determine if criteria for cirrhosis 1184 1185 were met and if death or graft loss was HCV-related. The cumulative distribution (or survival) function for time from transplant to cirrhosis will be estimated using either parametric models or 1186 nonparametric (Turnbull estimator) methods. To test for a difference in this distribution between 1187

- 1188 LDLT and DDLT, adjusting for covariates such as age and MELD score, parametric regression
- 1189 models (e.g., using SAS Proc Lifereg), or discrete survival analysis methods (e.g., using SAS Proc
- 1190 Genmod) will be used.
- 1191 In addition, times to patient death and graft failure will be analyzed as right-censored outcomes,
- 1192 using standard survival methods (Kaplan-Meier estimates, log rank tests, and Cox regression). Non-
- 1193 Markov multistate models⁷³ will be considered if feasible with the available data.
- 1194 Validation of transient elastography will be performed based on the subset of patient who undergo
- both transient elastography and biopsy within 90 days of each other. The correlation coefficient
- between transient elastography measure and Ishak score from biopsy will be calculated. A
- calibration model will be fit to convert transient elastography values into Ishak equivalents. A strong
- 1198 correlation (e.g., 0.7 or higher) would be expected if the two methods are to be considered
- 1199 interchangeable. A transient elastography cutpoint of values above 12.5 kPa are indicative of
- 1200 cirrhosis.

12014.6Primary Aim 6: To understand the history of pain management and to measure quality1202of care in pain control in living donors following partial hepatectomy.

1203 **4.6.1 Study Methods**

1204 The study uses two surveys to collect information about live donor pain management. The first 1205 survey collects information from care providers in the A2ALL Consortium regarding the details of 1206 their choice of pain management and their opinions/beliefs.

1207 4.6.1.1 Study Methods – Retrospective Component

1208 We used the APS-POQ-R as a template to develop the survey questions. The survey addresses 1209 aspects of practice that are linked to outcome, including: resources and personnel participating in 1210 pain management, methods used to assess pain, and opinions about the efficacy of pain management. 1211 An electronic retrospective survey (see Appendix E) will be distributed to the transplant research coordinator and completed by a surgeon, nurse and anesthesiologist (if the latter is involved in pain 1212 1213 management) at each of the nine A2ALL clinical centers. The survey measures the methods and personnel used in postoperative pain management, how pain was assessed and what quality 1214 1215 indicators were used assess performance. Data will be collected via a commercial web-based survey 1216 application.

1217 4.6.1.2 Study Methods – Prospective Component

1218 All sites will utilize the APOS-POQ-R (see Appendix F) to collect information about the outcome of 1219 pain management from the post-op liver donors' perspective. A study coordinator will read the 1220 questions to the subjects and record their answers 48 hours following liver donation surgery. A database will be constructed from the subjects' answers to the APS-POQ-R that is not biased by the 1221 1222 source of the data or the technique used for pain management. Data will be analyzed for overall 1223 effect by measuring patient satisfaction (how living donors rate the quality of their pain care). 1224 Answers to the survey questions assess overall patient satisfaction. The responses to individual questions that identify specific areas of pain management also relate to patient satisfaction. 1225

Collection and analysis of this data corresponds to our study's objectives summarized in Section 1226 1227 3.6.1.

1228 4.6.1.3 Participant Selection – Retrospective Component

- 1229 The lead investigator at each site will select up to three health care providers involved in post liver
- 1230 donation pain management: a liver transplant surgeon, an anesthesiologist, and the nurse transplant 1231 coordinator.
- 1232 4.6.1.4 Participant Selection – Prospective Component
- 1233 Inclusion Criteria

1234

- Adult living liver donors
- 1235 **Exclusion** Criteria
- 1236 History of chronic pain •
- History of narcotic use (routine scheduled narcotic use for treatment of a pain disorder 1237 1238 diagnosed and treated by a physician)
- 1239 Medically unstable at 48 hours post-donation surgery •
- 1240 Language barrier •
- 1241 4.6.1.5 Data elements
- 1242 **Retrospective Component:**
- 1243 Responses to retrospective survey (see Appendix E)
- **Prospective Component** 1244
- 1245 Demographic information as described in Section 4.1.3 •
- 1246 Intraoperative, perioperative and post-operative complication and hospitalization information • as described in Section 4.1.3 1247
- 1248 Responses to screening questions regarding history of chronic pain and narcotic use •
- Responses to the APS-POQ-R survey (see Appendix F) 1249 •
- 1250 4.6.1.6 Sample size and power calculations
- 1251 Retrospective Component: The unit of analysis is the clinical center, with a sample size of 9. This
- analysis will describe clinical practice at the 9 A2ALL centers and will not attempt to make 1252
- 1253 inference to a larger population.
- 1254 Prospective Component: We anticipate that approximately 200 future donors will be enrolled in 1255 A2ALL-2. Although it is unlikely that more than 200 donors will be accrued, enrollment will
- 1256 remain open during A2ALL-2 to allow as much power as possible to assess center effects and
- variables predictive of satisfaction with pain management. Because many of the study measures will 1257
- 1258 be presented descriptively, we first give the confidence interval (CI) width for, e.g., the true mean
- 1259 satisfaction score (0-10 scale) assuming a standard deviation of 2.0. With n=200, we will have 93%
- probability that the width of this CI will be no greater than +/-0.30. For comparing the satisfaction 1260 1261 scores at two of the 9 centers, say each with n=30 donors, we will have 90% power to detect a
- 1262 difference in means of 1.7. Sample size calculations were made using the SAS Power procedure
- 1263 (SAS Institute, Inc., Cary, NC).

1264 4.6.1.7 Statistical Analysis

- 1265 Retrospective Component:
- 1266 The methods and personnel that each center uses to manage postoperative pain in live liver donors
- 1267 and methods they have stopped using, will be presented using descriptive statistics. If possible,
- 1268 graphical methods will be used to display the changes over time.

1269 The medical specialty of care providers responsible for pain management and assessment will also

- be described for the 9 A2ALL centers. This summary will include both the type of specialists
 involved, and whether pain management involved an Acute Pain Team or not. Both the proportion
- 1271 of centers with Acute Pain Teams and the composition of these teams will be described. The
- 1273 continuity of pain management through phases of patient locations (e.g., ICU, surgical ward) will
- 1274 also be reported. Finally, the opinion of the medical care providers on the adequacy of pain control
- 1275 at their center will be described, and will also be compared to patient reports at that center (using
- 1276 data from prospective component of the study).
- 1277 Prospective Component:
- 1278 Satisfaction will be assessed using (a) the single question (P9), measuring overall satisfaction, and
- (b) the individual items of the pain questionnaire (P1-P8 and P10-12). These outcomes will be

1280 presented using descriptive statistics, including frequencies, means and standard deviations.

1281 Histograms and/or boxplots will be used to identify the forms of the distributions and to identify

- 1282 outliers. Aspects of care with low scores or a large standard deviation will be identified as practices
- 1283 that require overall improvement. Boxplots and analysis of variance will also be used to display and
- 1284 compare quality indicators from the APS-POQ-R measures by center.
- 1285 To identify aspects of care that account for differences in patient satisfaction, we will evaluate 1286 predictors of overall satisfaction (P9) using linear regression. Predictors of overall satisfaction to be
- 1287 tested will include the pain relief variables (P1-P7), participation in decisions about pain treatment
- 1288 (P8), helpfulness of information received (P10), non-medicine methods of treatment (P11, P12),
- 1289 demographic variables, and donor relationship.
- 1290 The complications outcomes (P6) will be analyzed using descriptive statistics as described above.
- 1291 Pain questionnaire data will also be linked to A2ALL-2 donor complication data to assess whether
- aspects of the donor pain experience, based on questions from the APS-POQ-R, are predictive of
- 1293 subsequent complications.

1294 **5 Human Subjects**

1295 **5.1 Protection of human subjects**

1296 5.1.1 Institutional review board

1297 This study and analysis will be performed under Institutional Review Board (IRB) oversight. Prior

to the initiation of the study, an IRB approval for study of human subjects will be obtained

separately from the IRB of each of the participating transplant centers and the DCC. Revisions to

the study protocol and changes in the study design will also be submitted to the individual IRBs for

approval prior to implementation.

- 1302 Subjects will be enrolled in the core protocol with full informed consent which will include the
- 1303 gathering of privileged health information (PHI), the collection of blood and tissue specimens
- 1304 beyond that normally performed for transplant/donation clinical care as well as samples for genetic
- 1305 studies, and the collection of medical and quality of life information at defined intervals prior to and
- 1306 after the transplant in donors and recipients.
- 1307 Each participating center will be responsible for obtaining such human subjects research
- 1308 authorization and will create an informed consent document detailing the procedures described
- above in the language required by their respective institutes. All key personnel at the participating
- 1310 centers will have successfully completed their IRB-required training and certification for human
- 1311 subject's research and HIPAA researchers' privacy requirements.
- 1312 5.1.2 Patient confidentiality

1313 **5.1.2.1 Core Protocol**

1314 Special procedures for ensuring patient confidentiality will be implemented. Data transmission and 1315 the distributed data systems have multiple layers of security as discussed below in Section 6, Study 1316 Management. Each study subject will be assigned an identification number. Only this number will be 1317 used to identify subjects in any individual tabulation. The PHI that is collected will represent the minimum necessary to successfully execute the study. The DCC plans to periodically update 1318 1319 outcomes and mortality information (graft failure, liver failure, mortality) in the study population by 1320 linking to the Scientific Registry of Transplant Recipients (SRTR). The DCC maintains a Data Use 1321 Agreement with the SRTR's contractor and adheres to the requirements set forth to protect subjects' privacy and confidentiality. Links to the SRTR database will be destroyed when the study has 1322 1323 ended.

1324 PHI entered into the database at the site level will only be visible to study personnel accessed

through a triple password regimen. The PHI is encrypted at the site level. Site personnel have the

- decryption key, and it is not available to the DCC. It is expected that only group data will be
- published. If individual subject data are to be published, no identifying information will be included.
 The study files will be maintained in a secure location as described above. Access to computerized
- 1329 data will be restricted to study personnel. Password authorization will be enforced. Previous use of
- 1330 this security system and secured server indicates that this technique is very successful in assuring the
- 1331 protection of confidential information.
- 1332 Authorized representatives of the Sponsor, the National Institute of Diabetes, Digestive and Kidney
- 1333 Diseases (NIDDK), National Institutes of Health (NIH), participating clinical institution, DCC
- 1334 monitoring staff, as well as the IRB, have access to medical records and records from participation in
- 1335 this study. Such access is necessary to ensure the accuracy of the findings.

1336 5.1.2.2 HRQOL Substudy

- 1337 Potential risks of the HRQOL substudies include a possible breach of confidentiality. Care will be
- taken at all stages of the protocol to ensure and protect study participants' confidentiality. Individual
- 1339 A2ALL sites will each assure, and their consent forms will explain, that the living donor transplant
- team and program will not be informed as to the contents of any completed HRQOL assessment
- 1341 instruments by study participants. No materials gathered during the research will become part of

1342 participants' medical records, including any records maintained by the living donor programs. No

1343 individual participant will be identified in any published report. Data collected during the research

1344 will be entered into password-secured databases by research staff authorized by the survey center PIs

- at Northwestern University (NWU) and the University of Pittsburgh (Pitt) to do this (see Section 6,
- 1346 Study Management, for further discussion of survey research center management issues). Research
- records and documents will be kept in a locked file. No research documents will contain the namesof study participants. Instead, identification numbers will be assigned to each study participant to
- 1349 mask their identity, and the list linking participant names and IDs will be stored in a separate locked
- 1350 file in the survey center PI's office. The study interviewers at the centralized survey research centers,
- 1351 who will perform HRQOL study assessments, will have study participant contact information but
- they will not be employed by the living donor programs and they will all sign a statement indicating
- 1353 that they will abide by HIPAA and IRB confidentiality regulations.

1354 **5.1.3** Risks to the study participant and adequacy of protection against risk

1355 Patients enrolled in this study will experience more than the normal amount of testing which is 1356 customary for this complicated medical and surgical procedure. Additional time will be required 1357 both before and after the transplant for the gathering of medical and quality of life information. 1358 Blood and liver tissue will be collected and stored for special tests which are not normally required 1359 for clinical care. Venipuncture carries risks of pain and bruising at the puncture site. Intraoperative biopsy carries the risk of increased bleeding. Percutaneous liver biopsy carries the risks of: pain 1360 1361 (20%), severe bleeding requiring a blood transfusion or an operation to stop the bleeding, infection, 1362 puncture of the gallbladder, lung or kidney (~1 per thousand), and death (~1 per 10,000). In addition 1363 to the risks associated with a percutaneous liver biopsy, a liver transjugular liver biopsy carries the 1364 following risks: collection of hemotoma in the neck, temporary problems with the facial nerves, and 1365 temporary voice problems. Portal and hepatic vein pressure and flow measurement also carries the 1366 risk of bleeding and damage to the vein(s). All research procedures will be carried out by qualified 1367 personnel who are experienced in performing the tasks.

1368 The study participant interviews and the HRQOL instruments do not involve any known physical 1369 risks. Individuals may experience psychological discomfort in answering repeated, longitudinal 1370 assessment questions related to their emotional well-being, health concerns and worries, relationship 1371 problems, or financial hardships. With respect to potential discomfort developing during 1372 interviewing, we note that the interviewers will be trained by the investigators to be sensitive to 1373 participant discomfort and concerns. Regarding the post-donation assessments in particular, we have 1374 found in our previous studies involving living donors that they often report that, rather than being 1375 stressful, post-donation assessments are a source of support to them and that they are glad to have 1376 had the chance to discuss the donation experience and post-donation issues. There is a potential risk 1377 of breach of confidentiality that is inherent in all research protocols and steps to minimize this risk 1378 are described above. Steps to minimize risk and address any psychological discomfort are addressed 1379 below.

1380Recruitment and Informed Consent. At each A2ALL site, individuals eligible for study1381(based on criteria described in Section 4.1.2 above) will be approached by a member of the1382living donor transplant team for release of their protected health information and contact1383information so that study staff may approach them to describe the study and obtain informed1384consent. All consent forms will be HIPAA compliant. A copy of the signed consent forms

will be kept by the study participant, and one will be kept in the research records at the site
where the participant was enrolled. Participants will be informed verbally and in the
informed consent form that their contact information will be released to a centralized survey
research center which will contact them and conduct the interviews by telephone. They will
be informed of the assessment time points and the payments they will receive for
participating in the HRQOL assessments.

